Academic Institution	Name: [name] Address: Manchester Metropolitan University, [name] Contact no: [name]

[figure not shown]
STUDY SUMMARY

Full study title	A comparative assessment of the relationship between the measurements made in an incremental shuttle walk test and an incremental cycle ergometry test in patients with idiopathic pulmonary fibrosis	
Short study title	ISWT vs CPET	
Study aim	
 1. To test the relationship between VO_2 peak in a CPET and the distance walked in an ISWT 2. To test the hypothesis that PO_2 is the same at the end of an ISWT and a CPET. 	
Study design	Single centre	
Study participants	Patients over the age of 16 with a confirmed diagnosis of IPF	
Study arms	Not applicable	
Sample size	43	
Planned study period	4 months	
Planned recruitment start date	1 st December 2017	
Planned recruitment end date	1 st March 2018	
Planned study end date	31 st March 2018	
	Objectives	Outcome Measures
Primary	To test the relationship between distance walked in an ISWT and VO_2 peak measured in a CPET.	VO_2 peak

Key Words: Idiopathic pulmonary fibrosis, cardiopulmonary exercise test, incremental shuttle walk test, VO_2 peak

STUDY FLOW CHART

Figure 1: Flow of participants through the study

SCHEDULE OF OBSERVATIONS

Table 1: Schedule of measures:

Schedule of events

Procedure	First meeting	Phone conversation	Second meeting	Visit one	Visit two
Eligibility Check	X				
Decision to take part in study or not to take part in study		X			
Informed consent			X		
Participant questionnaire			X		
Incremental shuttle walk test				X ^A	X ^B
Cardiopulmonary exercise test				X ^B	X ^A
Capillary blood gas				X	X

X – applies to all patients, whether in group A or group B.

X^A – patient randomly assigned to group A. These patients complete the ISWT at visit one and CPET at visit two.

X^B – patient randomly assigned to group B. These patients undertake CPET at visit one and ISWT at visit two.

LIST of CONTENTS

GENERAL INFORMATION	Page No.
TITLE PAGE	1
RESEARCH REFERENCE NUMBERS	1
SIGNATURE PAGE	2
KEY TRIAL CONTACTS	3
TRIAL SUMMARY	4
TRIAL FLOW CHART	5
SCHEDULE OF OBSERVATIONS	6
LIST OF CONTENTS	7
LIST OF ABBREVIATIONS	8
SECTION	
1. INTRODUCTION	9
2. TRIAL DESIGN	13
3. STUDY SETTING	13
4. ELIGIBILITY CRITERIA	14
5. TRIAL PROCEDURES	15
6. STATISTICS AND DATA ANALYSIS	16
7. DATA HANDLING	17
8. TRIAL OVERSIGHT	18
9. MONITORING, AUDIT & INSPECTION	18

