Current NICE guidelines (2013b) for IPF management recommend using resting measurements of spirometry and gas transfer to assess disease severity and likely prognosis. However, patients with IPF demonstrate significant exercise limitation due to impaired gas exchange and ventilation (Miki et al., 2003). Measurements made during exercise have been shown to be more sensitive to the changes in oxygen transfer associated with IPF than those made at rest (Ley et al. 2011). CPET is recognised as a gold standard test for IPF assessment but has not been routinely adopted in practice (Bonini and Fiorenzano, 2017).

A study of IPF by Kawut et al. (2005) showed that VO_2 peak in a maximal CPET was inversely proportional to a patient's risk of death. Similarly, Fell et al. (2009) found that a VO_2 peak of < 8.3 ml/kg/min in a CPET was associated with an increased risk of death in patients with IPF. Oxygen consumption during an incremental treadmill test and an ISWT increases similarly (Singh et al., 1994) and, because an ISWT is cheaper, quicker and easier to perform, the usefulness of measurements made during an ISWT should be evaluated in more detail.

Moloney et al. (2003) demonstrated a significant correlation between total distance walked in a corridor ISWT by patients with IPF and the VO_2 max measured during a shuttle walk test on a treadmill. In a previous study in our department the distance walked in an ISWT by patients diagnosed with IPF

ISWT vs CPET

correlated with the individual's VO_2 peak during an incremental cycle ergometry test (ICET) (Fielding et al., 2015). Linear regression was used to derive a formula which predicted VO_2 peak using ISWT distance. The present study looks to test this formula in a new cohort of patients with IPF.

Arterial oxygen pressure (PaO_2) at the end of a maximal CPET has also been shown to be a significant predictor of survival in patients with IPF (King et al., 2001). This study also investigates the relationship between blood oxygen pressure (PO_2) at the end of a CPET and the end of an ISWT.

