1.2 Proposed study

Patients at University Hospital, Coventry and St Cross Hospital, Rugby will be invited to take part in a letter. Those who express an interest in taking part will be given more information about the study including a written document and then at least 48 hours to decide whether or not to take part in the study. Should they decide to take part, each participant will be asked to make two visits to University Hospital Respiratory Physiology and Sleep Department.

At one visit participants will be asked to undertake an ISWT; walking 10 m between cones at an increasing speed dictated by a standardised audiotape. The ISWT will be performed according to the standardised protocol set out by Singh et al. (1992) and our department protocol. At the other visit participants will undertake an ICET. The ICET will be performed on a static exercise bike following the department protocol. The order in which these two tests are done will be randomly assigned to each participant.

After both the ISWT and the ICET, an earlobe capillary blood sample will be taken by a trained member of staff and the sample analysed for blood oxygen pressure. Each participant will also fill in a questionnaire about their experience of the test.

The relationship between ISWT distance and VO_2 peak will be analysed and the oxygen pressure of capillary blood gas after each test will be compared.

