1.3 Study population

This is a prospective study of patients with a diagnosis of IPF confirmed by a multi-disciplinary team. We aim to recruit a minimum of 43 patients to this study, all of whom will already be under the care of a Respiratory Consultant at University Hospitals Coventry and Warwickshire NHS Trust.

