2.2 Justification

This project tests a formula proposed by Fielding et al. (2015) to predict VO_2 peak during an ICET using distance walked in an ISWT. It will compare predicted VO_2 peak value with the actual value in a new cohort of patients with IPF. In addition, this study will test the relationship between PO_2 at the end of an ICET and at the end of an ISWT.

NICE recognises the importance of providing patients and their families with information when IPF is diagnosed and as the disease progresses (NICE, 2013b). Patients can be better informed about expectations of future symptoms and management, their treatment options and their life expectancy if more accurate prognostic tests are available.

This study paves the way for a relatively cheap and widely available incremental exercise test to be used to gather helpful information about a patient's prognosis. In the future, such a test could be recommended for making prognostic predictions in IPF.

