3 OBJECTIVES AND OUTCOME MEASURES/ENDPOINTS

3.1 Primary objective

To assess the relationship between VO_2 peak and ISWT distance and to determine how similar it is to a linear relationship from other data collected in a previous study with the following relationship:

$$\text{VO}_2 \text{ peak} = 10.02 + (0.01575 \times \text{ISWT distance})$$

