7.5 Statistical analysis

The data collected in this study will be combined with data from the previous study in our department and distinguished by a study indicator. The similarity between the two datasets will be tested using a series of linear regression models. The value of PO₂, measured in capillary blood, after ISWT and after CPET will be compared using a paired t-test. All analyses will be performed in SPSS statistical software. We do not anticipate missing data. Should a participant withdraw from the study then none of the identifiable data that they generated will be used.

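### The paired t-test can count against the hypothesis that PO2 is the same after the two exercise tests, but a non-significant result could not support it, and nothing else in the plan could

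*Combined protocol and SAP*

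**What the plan says.** The Study Summary and section 2.1 (Aims and hypothesis) both give the second of the two aims as "To test the hypothesis that PO_2 is the same at the end of an ISWT and a CPET".

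One sentence in section 7.5 (Statistical analysis) carries the whole PO2 analysis: the values "measured in capillary blood, after ISWT and after CPET will be compared using a paired t-test". Section 1.2 (Proposed study) adds only that "the oxygen pressure of capillary blood gas after each test will be compared". The other method in section 7.5, "The similarity between the two datasets will be tested using a series of linear regression models", concerns the new and previous datasets and is not assigned to PO2.

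Two other places word the PO2 aim more loosely. Section 1.1: "This study also investigates the relationship between blood oxygen pressure (PO_2) at the end of a CPET and the end of an ISWT". Section 2.2: "this study will test the relationship between PO_2 at the end of an ICET and at the end of an ISWT". Neither attaches a method.

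The sample size is given in section 1.3: "We aim to recruit a minimum of 43 patients to this study". No significance level, SD of the PO2 differences, important difference, margin or power is stated. PO2 does not appear in the primary objective (section 3.1, "To assess the relationship between VO_2 peak and ISWT distance" and its comparison with the earlier formula) or in the primary endpoint (section 3.2).

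**The concern.** A paired t-test is built to detect a mean difference. When p is below the threshold it gives evidence against equal means. When p is above it, the data may be compatible with no difference and also with a sizeable one, and the p-value does not tell these apart. The aim is worded in terms of sameness, so the outcome most likely to be reported as a positive answer is the one the test cannot support.

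No section says that non-significance will be taken as equality. None guards against it either: the plan has no interval, margin, agreement statistic or interpretation rule.

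What is at stake is how the PO2 result will be read. Section 1.1 presents arterial oxygen pressure at the end of a maximal CPET as a predictor of survival, and section 2.2 looks ahead to a cheaper exercise test giving prognostic information. An unsupported statement that PO2 was the same would suggest that the end-ISWT value can stand in for the end-CPET value.

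**Working it through.** **Inputs**

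- Pairs: n = 43 (Study Summary; sections 1.3 and 6 call it a minimum). Each participant does both tests in random order (section 1.2) and no missing data are expected (section 7.5), so 43 pairs and 42 degrees of freedom.
- Significance level: not stated. Assumed two-sided 5%.
- SD of the paired PO2 differences and important difference: not stated. Results are therefore in units of that SD.

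The figure of 43 cannot be reproduced, because the documents give no inputs for it.

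**1. How often a real shift would be non-significant**

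For a true mean shift of d SDs, the test statistic follows a non-central t with 42 df and non-centrality d × √43, where √43 = 6.557. The critical value is t(0.975, 42) = 2.018.

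| True shift (SD) | Non-centrality | P(non-significant) |
|---|---|---|
| 0 | 0 | 95.0% |
| 0.1 | 0.656 | 90.2% |
| 0.2 | 1.311 | 75.1% |
| 0.3 | 1.967 | 51.5% |
| 0.4 | 2.623 | 27.3% |
| 0.5 | 3.279 | 10.7% |

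Simulation with 400,000 replicates gave 75.0%, 51.4% and 27.2% for 0.2, 0.3 and 0.4 SD. Power reaches 80% at a shift of 0.437 SD and 90% at 0.506 SD.

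**2. Dependence on sample size**

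At a true shift of 0.3 SD, the chance of a non-significant result is 86.4% with 10 pairs, 75.3% with 20, 51.5% with 43 and 15.6% with 100. If non-significance were read as sameness, a smaller study would be more likely to find it.

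**3. What an interval would show**

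The 95% CI half-width is t(0.975, 42)/√43 = 2.018/6.557 = 0.308 sample SDs. At p = 0.05 exactly, the interval runs from 0 to 2 × 0.308 = 0.616 SD. A result just short of significance is therefore compatible with differences from about none to about 0.62 SD. The p-value alone does not show this.

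**4. What 43 pairs could support if equivalence were wanted**

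Equivalence on average is concluded if the 90% CI lies wholly inside ±margin (two one-sided 5% tests). The 90% half-width is t(0.95, 42)/√43 = 0.256 sample SDs. Power, integrated over the sampling distribution of the SD, with a true difference of zero:

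| Assumed margin (SD) | Power, 43 pairs |
|---|---|
| 0.2 | 0.1% |
| 0.3 | 23.2% |
| 0.4 | 65.0% |
| 0.45 | 79.2% (simulation 79.3%) |
| 0.5 | 88.6% |

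The smallest margin with 80% power is 0.454 SD if the true difference is zero, and 0.494 SD if it is 0.1 SD. For 80% power at a true difference of zero, a margin of 0.3 SD needs 97 pairs and 0.2 SD needs 216. All these margins are assumptions, since the documents give none.

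**The case against.** The best defence is that aim and test match as written. Testing the hypothesis that two means are the same is what a paired t-test does, with sameness as the null. The documents never promise to show equivalence or interchangeability of PO2; elsewhere they speak only of comparing the values or of their relationship. Failing to forbid a misreading is not in itself an error. The mean difference and its standard error are already components of the t-test, and software may print an interval anyway. The probabilities above would apply to any 43-pair t-test. PO2 is outside the primary objective and endpoint, section 4 describes a basic science study, and no decision rule depends on PO2 being equal.

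Much of this stands. The t-test is not the wrong test, a significant result would be valid, the harm depends on how a null result is reported, and the sizes are illustrative because no PO2 scale is given.

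It does not remove the gap. This is one of only two stated aims, its wording invites a conclusion of sameness, and the plan says nothing on how to read the outcome that would prompt that conclusion. An interval that software might print is not a commitment to report or interpret it. The looser wording about a relationship does not help, because a paired test of means does not assess a relationship either.

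**Conclusion.** The concern holds. As written, the plan can reject equality of mean PO2 but has no means of supporting it, and leaves a non-significant result without a valid interpretation. On the assumptions of 43 complete pairs and a two-sided 5% test, a true shift of 0.3 SD would be missed about half the time, and 80% power is reached only at about 0.44 SD. Whether shifts of that size matter clinically cannot be judged from the documents.

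This should be corrected before analysis. It affects a secondary aim only; the analysis of VO2 peak against ISWT distance is not touched.

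**What to change.** In section 7.5, keep the paired t-test sentence and add:

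> *The test will be two-sided at the 5% level, and the mean paired difference in capillary PO2 (ISWT minus CPET) will be reported with its 95% confidence interval. A non-significant difference will not be interpreted as equality.*

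In the Study Summary and section 2.1, reword the second aim along these lines:

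> *To estimate the difference in PO2 between the end of an ISWT and the end of a CPET.*

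Only if the sponsor wishes to claim sameness: fix a justified margin in PO2 units before data are seen, and conclude equivalence on average only if the 90% CI lies wholly within it. That would concern means; if agreement within individuals matters, limits of agreement would be needed as well.

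As an editorial matter, bring the references to a PO2 relationship in sections 1.1 and 2.2 into line with the comparison described in sections 1.2 and 7.5.

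The core change costs wording only, with no extra patients or measurements. The price is that no claim of sameness can be made without a prespecified margin. If one is set tighter than about 0.45 SD (0.49 SD if the true difference is 0.1 SD), 43 pairs give less than 80% power and the result may be that equivalence is not shown.

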7.6 End of study definition

The end of the study will be defined when the last participant has completed the last study visit.

8 DATA HANDLING

8.1 Data collection tools and source document identification

Identifiable information will be saved in one database for this study. Each participant will be assigned a research number for this study which will be linked to their personal information only in this one database. All other project files and data collection sheets will be anonymised; the participant will only be identified by their research number.

All members of the Respiratory Physiology and Sleep team who have access to the office undertake annual information governance training and work within the guidelines of the Data Protection Act 1998.

8.2 Data handling and record keeping

Screening and recruitment logs of all participants approached to take part in the study and enrolled in the study will be kept for the study. Participants that agree to participate in the study will be assigned a unique identifier, which will be used to identify all documents associated with that participant for the duration of the study. All data generated in the study will be kept on site at UHCW. Participant consent will be recorded, in triplicate, on an informed consent form and stored securely at UHCW.

8.3 Access to Data

Access to study data will be restricted to members of the study team and patient identifiable data will be restricted to those members of staff that require it for the performance of their role. Direct access to data

will be granted to authorised representatives of the Sponsor, host institution and the regulatory authorities for the purposes of trial-related monitoring, audits and inspections.

8.4 Archiving

Following the resolution of queries and confirmation of study close-out by the CI, all essential documentation will transferred to a third party archiving service, which provides suitable fire and water-resistant facilities. Study files will be archived for a period of 25 years. Access to the study documentation will be restricted to named individuals within the study team with express permission from the CI.

9. TRIAL OVERSIGHT

9.1 Role and responsibilities of the Sponsor

UHCW has agreed to act as sponsor for this trial and will undertake the responsibilities of sponsor as defined by the Research Governance Framework and ICH Good Clinical Practice. An authorised representative of the Sponsor has approved the final version of this protocol with respect to the trial design, conduct, data analysis and interpretation and plans for publication and dissemination of results. As sponsor, UHCW provides indemnity for this trial and, as such, will be responsible for claims for any non-negligent harm suffered by anyone as a result of participating in this trial. The indemnity is renewed on an annual basis and will continue for the duration of this trial.

10. MONITORING, AUDIT & INSPECTION

The study may be monitored by the Research & Development Department at UHCW as representatives of the Sponsor, to ensure that the study is being conducted as per protocol, adhering to Research Governance and GCP. The approach to, and extent of, monitoring will be specified in a trial monitoring plan determined by the risk assessment undertaken prior to the start of the study.

11. ETHICAL AND REGULATORY CONSIDERATIONS

11.1 Ethical approval and research governance

The study will be conducted in compliance the principles of the ICH GCP guidelines and in accordance with all applicable regulatory guidance, including, but not limited to, the Research Governance Framework. Ethical approval for this study will be sought from the Research Ethics Committee combined with HRA approval. No study activities will commence until favourable ethical opinion and HRA approval has been obtained. Progress reports and a final report at the conclusion of the trial will be submitted to the approving REC within the timelines defined by the committee. Confirmation of capacity and capability will be obtained from the R&D department prior to commencement of the study at all participating sites.

11.2 Data protection and patient confidentiality

The study will comply with the Data Protection Act 1998 and regular checks and monitoring will be undertaken by the Trial Manger to ensure compliance. Participants will be assigned a unique identifier upon enrolment in to the study to allow link-anonymisation of patient-identifiable data. Access to patient identifiable data will be restricted to members of the study co-ordination team who require it for the performance of their role. Electronic data will be stored on password protected encrypted drives and hard copies of study documents will be stored in locked filing cabinets in secure entry-card protected sites..

12 DISSEMINATION POLICY

The results of this study will be written up as a report. This report will be given to all Respiratory Consultants and patients will be able to discuss the results with their consultant. The results will also be written up as a research project which will be handed in as part of a Clinical Science Masters programme at Manchester Metropolitan University. If accepted for presentation, the results will be presented to members of the Association of Respiratory Physiology and Technology at their annual conference.

